
Study Design:
	
This is a randomized, open-label, 2-arm, parallel group study in approximately 20 healthy postmenopausal women with an intact uterus. This study is designed to assess the safety of DARE-HRT1 IVRs at two dose strengths, and the PK of progesterone, estradiol, and its metabolite estrone, from the IVRs. A preliminary assessment of the effect of DARE-HRT1 on VMS and on VVA signs and symptoms of menopause will be included. Screening procedures will ensure that participants are eligible, and will include a transvaginal ultrasound and, if needed, an endometrial biopsy and/or cervical screening test. Eligible participants with ongoing hormone replacement therapy at study entry will be required to undergo an appropriate washout period.
 
Randomization will occur prior to initiation of treatment and participants will be randomized in a 1:1 ratio to the following treatment groups.
 
  
 Treatment Group and Number of Participants	Treatment	
   
 IVR Dose 1 (N = 10)	12-week IVR 80/4 (estradiol 80 µg/day + progesterone 4 mg/day), replaced every 28 days	
 
 IVR Dose 2 (N = 10)	12-week IVR 160/8 (estradiol 160 µg/day + progesterone 8 mg/day), replaced every 28 days	
  
 
Participants will use DARE-HRT1 IVRs for 12 weeks, across three 28-day cycles, with a new IVR administered on Day 1 of each cycle. For each cycle, Day 1 is defined as the first day of treatment, i.e., the day the IVR is self-administered by the participant. Correct placement of the IVR will be confirmed by the study staff. The same IVR is to remain in position for 28 days, with removal of the IVR by the participant in the clinical research unit (CRU) on the morning of Day 1 of the next cycle. Participants will use a paper diary to document insertion and removal of the IVR and any instances of the IVR falling out, as well as any concomitant medication use.
 
In Cycle 1:
 
 • Baseline PK sampling will occur predose on Day 1 at -1, -0.5 and 0 (within 10 minutes) hours prior to insertion of the first IVR. Repeated blood sampling for PK will occur at 0.5, 1, 2, 4, and 8 hours following insertion. 
In Cycles 2 and 3:
 
 • Participants will return to the CRU on Day 1. During that visit, the IVR will be removed, blood will be drawn for PK (0 hours), and a new IVR inserted immediately (within 10 minutes) after blood was drawn. Repeated blood sampling for PK will occur at 0.5, 1, 2, 4, and 8 hours following insertion. 
In Cycles 1, 2, and 3:
 
 • On the mornings of Days 2 and 3, participants will return to the CRU for a single PK blood draw (24 and 48 hours following IVR insertion, respectively) • On the morning of Days 8, 15, and 22, participants will return to the CRU for a single PK blood draw and safety assessments 
In Cycle 3 only:
 
 • On the morning of Cycle 3, Day 29 (EOS), participants will return to the CRU for removal of the IVR. Repeated blood sampling will be performed before removal of the IVR (0 hours), and at 0.5, 1, 2, 4, and 8 hours after removal • Participants will return to the CRU the following day (Day 30) to provide a single PK blood sample 24 hours after IVR removal 	Treatment Group and Number of Participants	Treatment	IVR Dose 1 (N = 10)	12-week IVR 80/4 (estradiol 80 µg/day + progesterone 4 mg/day), replaced every 28 days	IVR Dose 2 (N = 10)	12-week IVR 160/8 (estradiol 160 µg/day + progesterone 8 mg/day), replaced every 28 days

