Endometrial biopsy ^d	X ^e															
Height (cm), weight (kg), and BMI ^f	X	X			X					X			X			
12-lead ECG	X															
Vital signs (BP and PR), RR, oral temperature	X	X		X	X		X	X	X	X		X	X			
Hematology and blood chemistry	X	X		X	X		X	X	X	X		X	X			
Urine dipstick	X	X			X					X			X			
FSH	X															

CONFIDENTIAL

Study Procedure	Screening	Cycle 1			Cycle 2					Cycle 3			EOS / ET		Follow-Up Phone Call
		Days -28 to -2	1	2, 3	8, 15, 22	1	2, 3	8	15	22	1	2, 3	8, 15, 22	29	
Serology tests ^g	X														
Drug and alcohol urine screen	X	X													
Training on use of IVR	X	X													
Randomization		X ^h													
Dispense IVR(s)		X			X					X					
Insert new IVR (after predose PK sample) ⁱ		X			X					X					
Remove used vaginal ring/return IVR(s)					X					X			X		
Confirm IVR placement		X ^j	X	X	X ^j	X	X	X	X	X ^j	X	X			
PK blood samples ^k	X	X ^l	X	X	X ^l	X	X	X	X	X ^l	X	X	X ^m	X ^m	
Usability and Tolerability questionnaire					X					X			X		
Vulvovaginal atrophy symptoms including most bothersome symptom		X											X		
MENQOL questionnaire		X											X		
Dispensing / Review of daily diary	X				X					X			X		
Adverse events, including serious adverse events	Adverse events and serious adverse events collected beginning at ICF signing and in an ongoing manner														
TEAEs	TEAEs collected beginning at IVR placement and in an ongoing manner as appropriate														
Prior/concomitant medications	X	Concomitant medications collected in ongoing manner, as appropriate													
Follow-up telephone call ^a															X

Abbreviations: AE = adverse event; BMI = body mass index; BP = blood pressure; ECG = electrocardiogram; EOS = end of study; ET = early termination; FSH = follicle-stimulating hormone; HCV = hepatitis C virus; HIV = human immunodeficiency virus; ICF = informed consent form; ID = identification;

CONFIDENTIAL

IVR = intravaginal ring; MENQOL = Menopause-specific Quality of Life; PK = pharmacokinetic; PR = pulse rate; RR = respiratory rate; SAE = serious adverse event; TEAE = treatment-emergent adverse events; temp = temperature.

- a. Participants undergoing washout of prior hormone replacement therapy will be required to sign the ICF before starting washout. Where washout of HRT will take approximately 8 weeks, screening procedures should not commence until 28 days prior to Cycle 1, Day 1.

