4 STUDY DESIGN

4.1 Study Design and Overview

This is a randomized, open-label, 2-arm, parallel group study in approximately 20 healthy postmenopausal women with an intact uterus.

This study is designed to assess the safety and tolerability of DARE-HRT1 IVRs at two dose strengths over 12 weeks of use, and to evaluate the PK of progesterone, estradiol, and its metabolite estrone, from the IVRs over this extended period. The study also includes a preliminary evaluation of the effect of DARE-HRT1 on VVA signs and symptoms (based on vaginal pH, vaginal cytology, and most bothersome symptom) and VMS (based on VMS questions in MENQOL). In addition, usability and tolerability will be assessed via a questionnaire.

Two treatment groups will be assessed in this study as shown in [Table 4-1](#).

Table 4-1: Treatment Allocations

Treatment Group	Number of Participants	Treatment
IVR Dose 1	10	12-week IVR 80/4 (estradiol 80 µg/day + progesterone 4 mg/day), replaced every 28 days
IVR Dose 2	10	12-week IVR 160/8 (estradiol 160 µg/day + progesterone 8 mg/day), replaced every 28 days

Participants who have been on prior HRT therapy will be required to complete the following washout period prior to randomization (for participants actively using HRT, washout may begin only after they have provided informed consent):

- 4 weeks or longer for prior transdermal estrogen alone or estrogen/progestogen products
- 8 weeks or longer for prior oral estrogen, oral estrogen/progestogen, or intrauterine progestogen therapy

Due to study enrollment goals and the length of the required washout periods, patients who are currently on progestogen implants or estrogen alone injectable drug therapy (requiring 3 months' washout) or estrogen pellet therapy or progestogen injectable drug therapy (requiring 6 months' washout) at the time of screening will not be enrolled.

Where washout of HRT will take approximately 8 weeks, screening procedures should not commence until 28 days prior to Day 1.

Upon completion of their screening procedures and confirmation of their eligibility, eligible participants will attend the clinical research unit (CRU) on the morning of Day 1.

Randomization will occur prior to initiation of treatment. Participants will be randomized in a 1:1 ratio to the two treatment groups ([Table 4-1](#)).

CONFIDENTIAL

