5.2 Exclusion Criteria

Participants will not be eligible for study participation if they meet any of the exclusion criteria, or will be discontinued at the discretion of the investigator in consultation with the medical monitor if they develop any of the exclusion criteria during the study.

1. Prior abnormal cervical screening test or Papanicolaou result within 2 years of screening. Participant can have atypical squamous cells of undetermined significance, if human papillomavirus negative.
2. Participants with any self-reported active sexually transmitted disease and/or evidence of infection based on vaginal visual examination by the investigator.
3. Participants with a urinary tract infection during screening as assessed by urine dipstick test with abnormal test findings (any positive result for leukocytes AND any positive result for nitrites).
4. Have a history of endometrial hyperplasia or cervical or uterine carcinoma.
5. Participants with indwelling catheters or requiring intermittent catheterization.
6. Participants with multiple or unsuccessful (e.g., still having symptoms) pelvic reconstructive surgery, or who suffer from pelvic relaxation.
7. Participants who have had a hysterectomy.
8. Participants taking any estrogen and/or progesterone products who are not willing to stop this treatment during their participation in this trial (see Section 4.1 for washout requirements). Participants who are using HRT that requires more than 8 weeks to wash out (e.g., progestogen implants or progestogen injectable drug therapy, estrogen alone injectable drug therapy or estrogen pellet therapy) will not be eligible.
9. Participants with concomitant use of personal lubricants (water-based lubricants are allowed) or any intravaginal product or medication, either by prescription or over-the-counter (OTC) (e.g., Femring [estradiol acetate vaginal ring], ESTRING[®] [estradiol vaginal ring]) with the exception of those who agree not to use these products during the IVR use period.
10. Self-reported or observed vaginal irritation unrelated to VVA; vaginal, vulvar, or cervical lesions, undiagnosed vaginal bleeding; or tenderness.
11. Participants with a finding of clinically significant uterine fibroids at screening.

CONFIDENTIAL

12. Participants with a known hypersensitivity to progesterone, estradiol, Femring, or the components of the IVR (e.g., ethylene vinyl acetate).
13. Participants with prior pelvic malignancies.

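### No washout interval is set for vaginal estrogen/progestogen products, so a recent user could have a treated VVA baseline on Cycle 1 Day 1

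*Combined protocol and SAP*

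**What the plan says.** Section 4.1 states the general rule: "Participants who have been on prior HRT therapy will be required to complete the following washout period prior to randomization". Two intervals follow: "4 weeks or longer for prior transdermal estrogen alone or estrogen/progestogen products" and "8 weeks or longer for prior oral estrogen, oral estrogen/progestogen, or intrauterine progestogen therapy". Current users of implants, pellets and injectables are not enrolled. Vaginal products are not in the list.

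Five other places bear on vaginal hormones:

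- **Exclusion 9** covers lubricants and intravaginal products, with Femring and ESTRING as examples. Users are excluded "with the exception of those who agree not to use these products during the IVR use period".
- **Exclusion 8** covers women taking any estrogen or progesterone product "who are not willing to stop this treatment during their participation in this trial (see Section 4.1 for washout requirements").
- **Inclusion 6** requires willingness to stop HRT and also points to Section 4.1.
- **Section 6.7.1** bars intravaginal products during the study unless the investigator prescribes them for a clinical event.
- **The Protocol Summary** says: "Eligible participants with ongoing hormone replacement therapy at study entry will be required to undergo an appropriate washout period".

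Table 1-1 allows screening from Day -28 to Day -2. Its footnote a says that women washing out HRT "will be required to sign the ICF before starting washout". VVA symptoms are first rated on Cycle 1 Day 1. Vaginal pH and cytology are taken at Screening and on Day 1. Section 7.6.2 says that PK baseline correction may be performed, using the mean of the three Day 1 predose concentrations.

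**The concern.** The study drug is a vaginal estradiol/progesterone ring, and the VVA endpoints are changes from a Day 1 baseline. Prior vaginal estrogen acts on the same tissue that those endpoints measure, yet it is the one admitted route with no stated interval. Inclusion 6 and Exclusion 8 defer to a list that omits it, and Exclusion 9 looks only at the period of ring use.

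There is no control group and there are 10 women per arm, so VVA effects are read as within-arm change. If a woman starts from treated pH, cytology and symptoms, she has less room to improve, and she is a tenth of her arm. For PK, residual estradiol in the predose samples would be subtracted as a constant although it is still falling, so later concentrations would be over-corrected. C_ss and C_max in each cycle are primary endpoints.

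**Working it through.** **1. Shortest time off product under the text**

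| Source | Days required off a vaginal hormone before Day 1 |
|---|---|
| Section 4.1 list | none stated |
| Exclusion 9 | 0 (applies during ring use) |
| Exclusion 8, Section 6.7.1 | none stated; stopping falls within participation or the study |
| Inclusion 6, Protocol Summary | a washout that is appropriate, not quantified |

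Read together, Exclusion 8 and Section 6.7.1 put stopping at or before screening. Screening may be as late as Day -2, so the shortest compliant interval is about 2 days.

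**2. VVA baseline**

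The documents give no time course for vaginal tissue after stopping estrogen, so no figure can be derived. Only the direction is clear: a treated baseline understates change. Symptoms have no rating before Day 1 that could reveal it.

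**3. PK, if baseline correction is applied**

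Inputs:

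- Prior Femring 0.05 mg/day, C_avg 40.6 pg/mL (Section 2.4.1).
- Baseline-adjusted estradiol C_ss 20.379 (Dose 1) and 30.920 (Dose 2) pg/mL, and Dose 1 C_max 143.655 pg/mL (Table 2-1).
- Half-life 30.775 h, the oral effective value in Table 2-2. *Applying it to a removed ring is an assumption*, because the documents give no post-removal half-life. The range shown is 15 to 60 h.

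Residual at Day 1 after d days off product = 40.6 × 2^(-24d / half-life). The residual is taken as gone by the C_ss window: from d = 7 it is 0.923 × 2^(-168/30.775) = 0.02 pg/mL a week later. The fall in corrected C_ss is then residual / C_ss.

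| Days off | Residual, pg/mL | Fall in Dose 1 C_ss (15 to 60 h) | Fall in Dose 2 C_ss |
|---|---|---|---|
| 2 | 13.77 | 67.6% (21.7% to 114%) | 44.5% |
| 7 | 0.923 | 4.5% (0.1% to 28.6%) | 3.0% |
| 14 | 0.021 | 0.1% (0.0% to 4.1%) | 0.07% |

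Other results:

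- **C_max:** at 7 days, 0.923 / 143.655 = 0.64% at most for Dose 1.
- **Arm level:** one such woman in 10 at 7 days moves the Dose 1 geometric mean C_ss by (1 - 0.0453)^0.1 - 1 = -0.46%.
- **Days for a fall under 5% in Dose 1 C_ss:** (30.775/24) × log2(40.6 / (0.05 × 20.379)) = 6.8 (3.3 to 13.3 over 15 to 60 h). With Femring 0.10 mg/day (C_avg 76.0 pg/mL) it is 8.0 (3.9 to 15.6).
- **At 28 days,** worst case (76.0 pg/mL, 60 h): 0.032 / 20.379 = 0.16%.

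**The case against.** The strongest reply is that stopping is already required. The criteria are cumulative, Exclusion 8 covers every estrogen or progesterone product, and Section 4.1.1 counts the 28-day screening period as participation. A reader might infer from Exclusion 9 alone that a woman may keep using her own ring until the study ring goes in. The documents do not support that. What stands is a missing number, which matters only when screening is short or the product was stopped late.

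A reader might also infer that the primary PK endpoints are seriously at risk, citing the 68% figure. That figure needs product stopped two days before Day 1, with screening compressed to the end of its window, and it needs a correction that is only optional. After a week off product the effect is small at the assumed half-life. It is no argument about ESTRING, because the documents give no PK for that product.

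Table 1-1 also provides a partial check. It marks pH, cytology and a PK sample at Screening, so a shift between Screening and Day 1 might be seen, although footnotes k and l do not describe the Screening PK sample. It does not help for symptoms.

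The VVA endpoints are exploratory, and Section 2.4.2 says that the study is not designed to show efficacy. This limits the severity but does not remove the gap, because preliminary VVA evaluation is a stated objective.

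Finally, a reader might extend the point to transdermal users, whose 4-week washout equals the screening window, so that the ultrasound could fall early in washout. The only timing rule is: "Where washout of HRT will take approximately 8 weeks, screening procedures should not commence until 28 days prior to Day 1". Nothing says that its purpose is a hormone-free scan. The extreme is a corner case, Inclusion 3 requires an acceptable biopsy above 4.0 mm, and the effect in mm cannot be derived. That extension is not supported as a finding.

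**Conclusion.** The gap is real and minor. Section 4.1 gives no interval for vaginal estrogen/progestogen products, and no other clause supplies one, so a compliant participant could reach Day 1 about 2 days off product. The main consequence is a treated VVA baseline, biased towards understating change and of unknown size.

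The PK consequence is conditional on baseline correction and on recent use of a systemic-dose ring. Under the Femring 0.05 mg/day and 30.775 h assumptions, it is about 4.5% of that woman's Dose 1 C_ss at 7 days and 0.1% at 14 days, and under 1% of C_max at 7 days. A slower true half-life would enlarge these figures: at 60 h, the 7-day figure is 28.6%. The documents do not show how many women would be affected, and it may be none.

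**What to change.** Add vaginal estrogen/progestogen products to the Section 4.1 washout list with a stated minimum before randomization. Four weeks would match the transdermal rule. A shorter interval would also serve if clinically justified: PK alone needs about 16 days in the worst case computed here, but recovery of vaginal tissue is a clinical judgement that these documents do not inform. Amend Exclusion 9 so that hormonal vaginal products must meet that washout, while non-hormonal products keep the present rule.

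This is amendment wording only, with no new procedure, sample or participant. The cost is later entry, up to about 4 weeks, for some vaginal-product users.

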5.3 Participant Re-enrollment

Participants who screen-fail from the study prior to randomization and study product administration may be rescreened and re-enrolled as long as the participant was not screen-failed due to noncompliance with the protocol (i.e., positive urine drugs of abuse screen, etc.). The medical monitor must be consulted prior to rescreening any participant. If the participant is rescreened, she must be reconsented and a new participant number must be used.

5.4 Participant Withdrawal

Participants are free to discontinue the study at any time, for any reason, and without prejudice to further treatment. The investigator may remove a participant if, in the investigator's judgment, continued participation would pose unacceptable risk to the participant or to the integrity of the study data. All procedures for early termination must be completed. Reasons for removal or withdrawal may include:

- Withdrawal of consent
- Administrative decision by the investigator or sponsor
- Ineligibility
- Significant protocol deviation
- Participant noncompliance
- Safety concern by the investigator or sponsor
- Lost to follow-up

Participants who are withdrawn prior to completing all study visits may be replaced.

In the event of a participant's withdrawal, the investigator will promptly notify the sponsor and medical monitor and will make every effort to complete the EOS assessments. All withdrawn participants with ongoing clinically significant clinical or laboratory findings will be followed until the finding is resolved or medically stable; reasonable attempts will be made to follow-up with participants.

5.5 Early Termination of Study

The study may be terminated at any time by the sponsor if serious side effects occur, if potential risks to study participants are identified, if the investigator does not adhere to the protocol, or if, in the sponsor's judgment, there are no further benefits to be achieved from the study. In the event that the clinical development of the study product is discontinued, the sponsor shall inform all investigators/institutions and regulatory authorities.

CONFIDENTIAL

6 TREATMENT OF PARTICIPANTS

6.1 Identity of Study Products

A description of the study products is presented in [Table 6-1](#).

Table 6-1: Study Products

Treatment Group and Number of Participants	Treatment
IVR Dose 1 (N=10)	12-week IVR 80/4 (estradiol 80 µg/day + progesterone 4 mg/day), replaced every 28 days
IVR Dose 2 (N=10)	12-week IVR 160/8 (estradiol 160 µg/day + progesterone 8 mg/day), replaced every 28 days

DARE-HRT1 IVRs will be sourced by Daré Bioscience Australia Pty LTD.

6.2 Treatments Administered

Each participant will be assigned to receive an IVR (Dose 1 or Dose 2) for 12 weeks, across three 28-day cycles, with a new IVR administered on Day 1 of each cycle. In Cycles 2 and 3, the new IVR should be self-administered as soon as possible after the previous IVR has been removed.

For each cycle, Day 1 is defined as the first day of treatment, i.e., the day the IVR is self-administered by the participant. Correct placement of the IVR will be confirmed by the study staff. The same IVR is to remain in position for 28 days, with removal of the IVR by the participant in the CRU on the morning of Day 1 of the next cycle.

If a participant cannot self-insert the IVR, the site physician will insert the IVR.

At the end of each cycle, participants will remove their own IVR.

6.3 Method of Assigning Participants to Treatment Groups

ICON will prepare the randomization scheme in accordance with its standard operating procedures (SOPs) and the randomization plan, which reflect Good Clinical Practice (GCP) standards. Refer to [Section 9.3](#) for a description of randomization methods. Eligible participants will be assigned to a treatment group according to the list of participant randomization assignments.

6.4 Measurements of Treatment Compliance

Treatment compliance of study product administration will be confirmed by PK evaluation and participant daily diary.

CONFIDENTIAL

6.5 Investigational Product Storage, Accountability, and Retention

6.5.1 Storage Conditions

The IP is to be stored at refrigerated temperature (2°C to 8°C). The product does not need protection from light. Additional information can be found in the Investigator's Brochure.

The investigator will ensure that all the study products are stored and dispensed in accordance with local regulations concerning the storage and administration of investigational drugs.

6.5.2 Study Product Accountability and Retention

The investigator must ensure that all study product supplies are kept in a secure locked area with access limited to those authorized by the investigator. The investigator must maintain accurate records of the receipt of all study products shipped by Daré Bioscience Australia Pty LTD or their representative, including but not limited to the date received, lot number, expiration date, amount received, and the disposition of all study products. Current dispensing records will also be maintained including the date and number of study products dispensed and the participant receiving the product. All remaining study products not required by regulations to be held by the CRU must be returned to Daré Bioscience Australia Pty LTD or their representative immediately after the study is completed.

It is the responsibility of Daré Bioscience Australia Pty LTD to ship a sufficient number of dosage units to allow the CRU to maintain an appropriate sampling on-site as per applicable regulatory requirements. Each reserve sample shall consist of a sufficient quantity to permit the local regulatory agency to perform 5 times all of the release tests required in the application or supplemental application.

